**Results of the Nasopharyngeal Swab**

Results of the nasopharyngeal swab may be received as soon as one day after testing.

If the PCR results are positive for SARS-CoV-2 infection at enrollment, the participant will be asked to remain in the study, administer study drug as per protocol, comply with all required testing for safety, and complete the remaining visits. If the participant does not want to administer study drug or complete testing, they will be asked to consent to telephone contact for the remaining visits.

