#### **7.1.6 Abnormal Laboratory Value**

Grade 2 and higher laboratory abnormalities (e.g., serum chemistry, CBC) are to be recorded.

Any laboratory abnormality that is new in onset or worsened in severity or frequency from the baseline condition and meets one of the following criteria will be recorded as an AE:

- Requires therapeutic intervention or diagnostic tests
- Leads to discontinuation of study treatment
- Has accompanying or inducing symptoms or signs
- Is judged by the investigator as clinically significant

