## 2. STUDY OBJECTIVES

### 2.1. Primary Objectives

The primary objectives of the study are to evaluate the safety and tolerability of GLS-1200 topical nasal spray as well as the incidence in the diagnosis of PCR-confirmed SARS-CoV-2 infection by treatment group.

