### 9.1.5. Summaries of Adverse Events

An overall summary of AEs will display, by treatment, the number and percentage (with 95% exact binomial confidence interval) of subjects who had any TEAE, whose strongest TEAE relationship to study drug is related or not related, whose maximum TEAE severity is mild, moderate, or severe, who had any SAE, any Serious TEAE, any TEAE leading to study discontinuation, and any TEAE leading to death.

The following summaries (number and percentage of subjects) of AEs (by SOC and PT) will be provided by treatment:

- All TEAEs
- All TEAEs by strongest relationship
- All TEAEs by maximum severity grade
- All Serious AEs
- All Serious TEAEs
- All TEAEs leading to study discontinuation
- All TEAEs leading to death

These summaries will present the number and percentage of subjects with at least one qualifying AE. Subjects may have more than one AE per SOC and PT. Each summary will be ordered by descending order of incidence of SOC and PT within each SOC.

In addition to the by-treatment summaries, data listings will be provided for the following:

- All AEs (with a flag indicating whether the event is treatment emergent)
- SAEs
- AEs leading to study discontinuation
- Deaths

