**List of Tables**

ICH Heading	Table Number	Table Description
14.1		DEMOGRAPHIC/BASELINE DATA
	14.1.1.1	Subject Disposition (All Subjects)
	14.1.1.2	Reason For Screen Failure (All Screen Failure Subjects)
	14.1.2	Demographic and Baseline Characteristics (Safety Population)
	14.1.3	Medical History (Safety Population)
	14.1.4	Concomitant Medications (Safety Population)
	14.1.5	Exposure and Treatment Compliance (Safety Population)
14.2		EFFICACY DATA
	14.2.1.1	Incidence of SARS-CoV-2 Infection by Visit (ITT Population)
	14.2.1.2	Incidence of SARS-CoV-2 Infection by Visit (PP Population)
	14.2.2	Incidence of Individual Symptoms and Average Number of Days with Symptoms by Visit Interval (ITT Population)
	14.2.3	Cumulative Incidence of SARS-CoV-2 Seroconversion by Visit (ITT Population)
14.3		SAFETY DATA
14.3.1		Displays of Adverse Events
	14.3.1.1	Overall Summary of Adverse Events (Safety Population)
	14.3.1.2	Treatment-Emergent Adverse Events by System Organ Class and Preferred Term (Safety Population)
	14.3.1.3	Treatment-Emergent Adverse Events by System Organ Class, Preferred Term, and Strongest Relationship to Study Drug (Safety Population)
	14.3.1.4	Treatment-Emergent Adverse Events by System Organ Class, Preferred Term, and Maximum Severity Grade (Safety Population)
	14.3.1.5	Related Treatment-Emergent Adverse Events by System Organ Class, Preferred Term, and Maximum Severity Grade (Safety Population)
14.3.2		Serious and Significant Adverse Events
	14.3.2.1	Serious Adverse Events by System Organ Class and Preferred Term (Safety Population)
	14.3.2.2	Serious Treatment-Emergent Adverse Events by System Organ Class and Preferred Term (Safety Population)

ICH Heading	Table Number	Table Description
	14.3.2.3	Treatment-Emergent Adverse Events Leading to Study Discontinuation by System Organ Class and Preferred Term (Safety Population)
	14.3.2.4	Treatment-Emergent Adverse Events Leading to Death by System Organ Class and Preferred Term (Safety Population)
14.3.4		Laboratory
	14.3.4.1	Shift from Baseline in Hematology Results by Test and Visit (Safety Population)
	14.3.4.2	Shift from Baseline in Chemistry Results by Test and Visit (Safety Population)
	14.3.4.3	Observed and Change from Baseline in Vital Sign Results by Test and Visit (Safety Population)

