## **APPENDIX C: TABLE LAYOUTS**

Table 14.1.1.1  
Subject Disposition  
(All Subjects)

Study Site Subject Status	GLS-1200	Placebo	Overall
Overall			
Screened			xx
Screen Failures			xx
ITT Population [1]	xx	xx	xx
Safety Population [2]	x (xx.x%)	x (xx.x%)	x (xx.x%)
PP Population [3]	x (xx.x%)	x (xx.x%)	x (xx.x%)
Completed the study [4]	x (xx.x%)	x (xx.x%)	x (xx.x%)
Discontinued the study	x (xx.x%)	x (xx.x%)	x (xx.x%)
Reason for discontinuation			
<Reason #1>	x (xx.x%)	x (xx.x%)	x (xx.x%)
<Reason #2>	x (xx.x%)	x (xx.x%)	x (xx.x%)
<Reason #3>	x (xx.x%)	x (xx.x%)	x (xx.x%)
Site 101			
.			
.			
Site 108			
.			
.			

Percentages are based on the ITT Population.

[1] The Intent-to-treat (ITT) Population includes all randomized to treatment allocation.

[2] The Safety Population includes all subjects who received at least one dose of study treatment.

[3] The Per-protocol (PP) Population includes all subjects who completed the trial, received  $\geq 90\%$  of the study treatments, and have no significant protocol deviations. Trial completion is defined as either completing Week 4 or meeting the study endpoint of PCR confirmed SARS-CoV-2 infection.

[4] Study completion is defined as completing all visits regardless of drug compliance.

Reference: Listing 16.2.1

Source: \\xx\\xx\\xx\\xx\\xx\\xxxx\\xxxxxxxxxxxx\\xxxx\\xxxx.sas      date      time

**Programming note:** Sort discontinuation reasons by descending overall frequency. List all reasons per CRF page.

Table 14.1.1.2  
Reason for Screen Failure  
(All Screen Failure Subjects)

Study Site	Reason	Overall (xx)
Overall		
<Reason #1>		x (xx.x%)
<Reason #2>		x (xx.x%)
<Reason #3>		x (xx.x%)
Site 101		
<Reason #1>		x (xx.x%)
<Reason #2>		x (xx.x%)
<Reason #3>		x (xx.x%)
Site 108		
<Reason #1>		x (xx.x%)
<Reason #2>		x (xx.x%)
<Reason #3>		x (xx.x%)

Reference: Listing 16.2.3 and Listing 16.2.1

Source: \\xx\\xxx\\xxx\\xxx\\xxxxxx\\xxxxxxxxxxxx\\xxxx\\xxxxx.sas      date      time

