**Programming Note: Continue for each individual symptom.**

Table 14.2.3  
Cumulative Incidence of SARS-CoV-2 Seroconversion by Visit  
(ITT Population)

Visit Seroconverted	GLS-1200 (N=XX)	Placebo (N=XX)
Week 2		
n	x	x
Yes	x (xx.x%)	x (xx.x%)
No	x (xx.x%)	x (xx.x%)
Week 4		
n	x	x
Yes	x (xx.x%)	x (xx.x%)
No	x (xx.x%)	x (xx.x%)
Week 6		
n	x	x
Yes	x (xx.x%)	x (xx.x%)
No	x (xx.x%)	x (xx.x%)

The incidence of seroconversion is summarized based on results obtained at or prior to the visit.

Reference: Listing 16.2.6.3

Source: \\xx\xxx\xxx\xxx\xxxxx\xxxxxxxxxxxxx\xxxx\xxxx.sas      date      time

Table 14.3.1.1  
Overall Summary of Adverse Events  
(Safety Population)

	GLS-1200 (N=XX) n (%) [95% CI]	Placebo (N=XX) n (%) [95% CI]
Subjects with any TEAE	x (xx.x%) [xx.x% - xx.x%]	x (xx.x%) [xx.x% - xx.x%]
Subjects whose strongest TEAE relationship to study drug is related [1]	x (xx.x%) [xx.x% - xx.x%]	x (xx.x%) [xx.x% - xx.x%]
Subjects whose strongest TEAE relationship to study drug is not related [2]	x (xx.x%) [xx.x% - xx.x%]	x (xx.x%) [xx.x% - xx.x%]
Subjects whose maximum TEAE severity grade is Mild [3]	x (xx.x%) [xx.x% - xx.x%]	x (xx.x%) [xx.x% - xx.x%]
Subjects whose maximum TEAE severity grade is Moderate [3]	x (xx.x%) [xx.x% - xx.x%]	x (xx.x%) [xx.x% - xx.x%]
Subjects whose maximum TEAE severity grade is Severe [3]	x (xx.x%) [xx.x% - xx.x%]	x (xx.x%) [xx.x% - xx.x%]
Subjects with any SAE	x (xx.x%) [xx.x% - xx.x%]	x (xx.x%) [xx.x% - xx.x%]
Subjects with any serious TEAE	x (xx.x%) [xx.x% - xx.x%]	x (xx.x%) [xx.x% - xx.x%]
Subjects with any TEAE leading to study discontinuation	x (xx.x%) [xx.x% - xx.x%]	x (xx.x%) [xx.x% - xx.x%]
Subjects with any TEAE leading to death	x (xx.x%) [xx.x% - xx.x%]	x (xx.x%) [xx.x% - xx.x%]

AE = adverse event; SAE = Serious Adverse Event; TEAE = Treatment-Emergent Adverse Event; CI = Confidence Interval

The 95% CIs for the subject percentages are calculated using an exact binomial distribution.

[1] Related TEAEs are those with a relationship of related, possibly related, or probably related. If the relationship is missing, it is considered related.

[2] Not related TEAEs are those with a relationship of unlikely related or not related.

[3] Severity grades are determined according to the NCI Common Terminology Criteria for Adverse Events version 5.0.

Reference: Listing 16.2.7.1

Source: \\xx\\xxx\\xxx\\xxx\\xxxxxx\\xxxxxxxxxxxx\\xxxx\\xxxx.sas

date      time

Table 14.3.1.2  

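### Adverse events that make a participant leave the study are tabulated, but those that only make a participant stop the spray are not, although tolerability is a primary objective

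*SAP*

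**What the plan says.** SAP 2.1 makes it a primary objective to "evaluate the safety and tolerability of GLS-1200 topical nasal spray", alongside PCR-confirmed infection. Protocol 2.2 does the same.

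For adverse events that end participation, SAP 9.1.5 has one category besides death. The overall summary closes with "any TEAE leading to study discontinuation, and any TEAE leading to death", and the list of SOC/PT summaries has "All TEAEs leading to study discontinuation". The shell of Table 14.3.1.1 repeats it as "Subjects with any TEAE leading to study discontinuation". Table 14.3.2.3 is the only SOC/PT discontinuation table in the Appendix B index, and Listing 16.2.7.3 uses the same criterion.

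The disposition shell, Table 14.1.1.1, has rows for completing and for discontinuing the study, and none for discontinuing treatment. Its footnote 4 reads: "Study completion is defined as completing all visits regardless of drug compliance". Protocol 4.4 defines completion differently: the participant must complete both the scheduled treatments and the follow-up visits.

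The protocol treats stopping the drug as an event of its own. Section 7.1.6 makes a new or worsened laboratory abnormality an adverse event if, among other criteria, it "Leads to discontinuation of study treatment". Section 7.3.1 has the site and sponsor discuss whether dosing should continue after an event requiring expedited reporting. Section 1.4 has staff discuss continued use of the atomizer if it causes discomfort. Section 7.2 requires the action taken to be recorded for every adverse event.

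**The concern.** Stopping a self-administered nasal spray because of an adverse event is direct evidence on tolerability. Protocol 1.4 states that the adverse effects of topical quinine are not known, so a reader of the study report will look for how many participants stopped the product because of one. The planned tables answer a different question: how many left the study because of one. If some participants stop the spray and keep attending visits, the planned row can be at or near zero in an arm where several people gave up the product for an adverse event. Nothing in the tables would show that the two counts differ.

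**Working it through.** The documents state no figure for this, so there is none to reproduce. The check has two parts.

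**1. Follow one participant through the planned output.** Suppose a GLS-1200 participant has a nasal adverse event, stops the spray after 7 days, attends Weeks 2, 4 and 6, and is not recorded as having discontinued the study.

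- *Disposition (Table 14.1.1.1):* counted as completed, by footnote 4.
- *Discontinuation row (Table 14.3.1.1) and SOC/PT table (14.3.2.3):* not counted, because the participant did not leave.
- *All-TEAE, relationship and severity tables (14.3.1.2 to 14.3.1.5):* the event is counted where it qualifies, with no sign that it ended treatment.
- *Exposure and compliance (SAP 7.6 and 7.7, Table 14.1.5):* with a complete diary, compliance is 7 × 3 / (28 × 3) = 21/84 = 25%, in the lowest band. No reason is attached, so this cannot be told apart from forgetting or loss of interest.
- *Exposure duration:* Appendix A (Stop Dates) sets the treatment stop date to start + 28 days if the diary has gaps of more than 3 days, or if it is missing in someone recorded as completing the study. In either case the early stop can also disappear from the duration of exposure.
- *PP population (SAP 6.3):* at 25% of doses the participant is excluded if no infection was diagnosed, again with no reason shown.
- *Listings 16.2.7.1 and, if serious, 16.2.7.2:* Action Taken and Study Discontinuation are separate columns. The second feeds a table; the first does not.

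The separate columns and footnote 4 both indicate that the SAP does not use study discontinuation as loose wording for stopping drug.

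**2. Size, under an assumed range.** Inputs: n = 150 on GLS-1200 (Protocol Table S1) and the exact binomial interval that SAP 9.1.5 specifies. The number x who stop the spray for an adverse event and stay is an assumption, because the documents give no expected rate. Assume also that nobody leaves the study for an adverse event.

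The Clopper-Pearson limits are: lower = the 0.025 quantile of Beta(x, n − x + 1); upper = the 0.975 quantile of Beta(x + 1, n − x). For x = 0 the lower limit is 0 and the upper is 1 − 0.025^(1/150) = 0.0243.

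| Stopped spray and stayed (assumed) | Planned row | Drug-discontinuation row (exact 95% CI) |
|---|---|---|
| 1 of 150 | 0% (0 to 2.4%) | 0.7% (0.02 to 3.7%) |
| 3 of 150 | 0% (0 to 2.4%) | 2.0% (0.4 to 5.7%) |
| 6 of 150 | 0% (0 to 2.4%) | 4.0% (1.5 to 8.5%) |
| 12 of 150 | 0% (0 to 2.4%) | 8.0% (4.2 to 13.6%) |

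From 6 of 150 upward, the point estimate of the missing row lies above the upper limit of the planned one (4.0% and 8.0% against 2.4%). At 12 of 150 the two intervals do not overlap.

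**The case against.** The strongest reply is that Protocol 4.4 already closes the gap. It ties completion to taking all scheduled treatments and lists adverse events among the categories of early termination. On that reading, someone who stops the spray for an adverse event can be recorded as an adverse-event termination, and the planned row would count them. This stands as a possible reading. But the tables are programmed from the SAP, and footnote 4 of Table 14.1.1.1 says the opposite. The count then depends on which definition a site or programmer applies, so the two need reconciling.

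A reader might also infer more than the documents support:

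- *That the tolerability tables count nothing but study discontinuations.* They do not. All-TEAE, relationship, severity and serious-event tables are planned by arm, with exact intervals in the overall summary. Only the subset that ended treatment is missing.
- *That better retention makes the understatement worse.* The effort in Protocol 4.4 to obtain all assessments is directed at people who have already discontinued the study. It is not a stated policy of keeping people in follow-up after they stop drug.
- *That the telephone follow-up in Protocol 6.5 shows adverse-event stops being retained.* It concerns only participants who are PCR-positive at enrollment and decline drug or testing.
- *That side effects noted in the diary reach only a listing.* SAP 7.6 does list them, but Protocol 7.2 and 9.6 require all adverse events to be recorded, and diaries are reviewed at visits. Those meeting the adverse-event definition should therefore reach the TEAE tables.

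It is also fair to say that early stopping is partly visible in Table 14.1.5. That stands for the number of doses, but the table does not give the reason.

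**Conclusion.** The point holds as a reporting gap. The SAP has no row or table for TEAEs that led to stopping study drug. Under its own definition of completion, a participant who stops for an adverse event and stays is tabulated as a completer with no discontinuation event.

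The size cannot be known in advance. Under the assumed range the planned row reads 0% where 0.7% to 8.0% of the active arm stopped the product for an adverse event. This rests on two assumptions: that 1 to 12 of 150 stop and stay, and that none leaves the study for an adverse event. If everyone who stops the spray is also recorded as leaving, the two counts agree and nothing is lost.

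No hypothesis test, analysis population or primary efficacy result changes. The change is still worth making because it bears on a primary objective and costs very little.

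**What to change.** 1. In SAP 9.1.5 and Table 14.3.1.1, add a row for subjects with any TEAE leading to permanent discontinuation of study drug, whether or not they left the study, by arm and with the exact 95% interval already planned for that table.
2. Add one SOC/PT table on the same criterion beside Table 14.3.2.3. Keep the study-discontinuation row and table as they are.
3. Derive both from Action Taken, after confirming that the CRF codes withdrawal of study drug and separates it from temporary interruption. The CRF is not among the documents and the listing shell shows only placeholder text, so this coding is unverified. If the field does not carry it, the SAP should say so and name the source to be used.
4. Reconcile the definitions of completion in Protocol 4.4 and footnote 4 of Table 14.1.1.1, so that a stop of drug is classified in the same way at both sites and in the programs.

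The cost is one row, one table and a clarified definition. If the coding is as expected, no new data are collected and no trial procedure changes.

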### 9.2. Clinical Laboratory Evaluations

Shift from baseline in laboratory parameter results (indicated as Low, Normal, or High) will be summarized for each post-baseline visit. Mean (+/- SD) laboratory parameter values will be graphically presented over time by treatment. All laboratory parameters will be listed and include indicators for low/high and clinical significance as determined by the investigator.

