### 1.4 Risk/Benefit Assessment

In accordance with the International Conference on Harmonization (ICH), this study has been designed to minimize the risk to study participants. Quinine treatment in this study does not replace or change everyday precautions taken by the study participants in preventing SARS-CoV-2 infection.

Quinine sulfate, dihydrate exposure in this study is 6 mg/day (1 ml of a 1 mg/ml solution used to irrigate each nostril, for total exposure of 2 mg per application, three times daily) and is similar to that used by [Desrosiers et al.](#) to study tobramycin vs saline placebo (where the placebo contained 1 mg/ml of quinine to mask taste) [37]. Doses ranging from 2.5 to 90 mg/day have been used as part of various studies for CF ([Table 1.1.2-1](#)). As reviewed above, the amount of quinine in an 8 oz. glass of tonic water is greater than 25 mg, while typical doses of quinine prescribed for leg cramps is 200-300 mg/day and for malaria is 1800 mg/day (600 mg three times daily).

The adverse effects of topical quinine are unknown. The adverse effects of orally prescribed quinine include hematologic changes (thrombocytopenia as most common and less commonly anemia) and electrocardiographic effects (particularly prolongation of the QTc). As reviewed, prior clinical studies of nasal or aerosol administered quinine in approximately 750 persons ([Table 1.1.2-1](#)) showed no quinine-associated adverse events.

The atomizer provided as part of this study is designed to provide a fine spray into the nose. There is the possibility that the atomizer will not function properly and will cause discomfort when used. Should this occur, study participants are asked to notify the study staff before their next dose. The study staff will discuss continued usage of the atomizer with the participant.

If the GLS-1200 or saline are accidentally sprayed into the eyes, ears or mouth, irritation may occur that could require evaluation. If the syringe and atomizer are not fully connected, the study participant may only receive a partial amount of study drug. If the atomizer or syringe packaging

is found to be open prior to use, it is possible that either component could be contaminated and thus there is a risk for infection. Devices with damaged packaging should not be used.

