### **8.3.2 Laboratory Data**

Continuous response variables per time point and changes from baseline will be summarized with mean, median, minimum, and maximum values. Categorical response variables will be summarized per time point with percentages.

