### **9.4. ECG Results**

Shift from baseline in 12-Lead ECG overall interpretation (results are Normal, Abnormal Not Clinically Significant (NCS), or Abnormal Clinically Significant (CS)) will be summarized at each post-baseline visit by treatment. Mean (+/- SD) continuous ECG parameter values will be graphically presented over time by treatment.

Additionally, the number and percentage of subjects will be summarized for the following QTcF Interval result categories at baseline and each post-baseline visit by treatment:

- <=450 msec (males) or <=470 msec (females)
- >450 msec (males) or >470 msec (females)
- Change from baseline <=60 msec (only applies to Week 4)
- Change from baseline >60 msec (only applies to Week 4)

A listing of ECG results will present the interpretations of abnormalities and whether these are considered clinically significant by the investigator.

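### SAP 9.2 omits, without saying so, the numeric change-from-baseline laboratory summary that Protocol 8.3.2 requires, and QTcF has no numeric change table either

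*SAP*

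**What the plan says.** **Protocol.** Section 8.3.2 sets the laboratory analysis: "Continuous response variables per time point and changes from baseline will be summarized with mean, median, minimum, and maximum values". Section 7.3 lists changes in laboratory parameters among the safety assessments. Section 1.4 says that the effects of topical quinine are unknown. For oral quinine it names "hematologic changes (thrombocytopenia as most common and less commonly anemia") and ECG effects, chiefly QTc prolongation. Safety and tolerability are a primary objective (2.2). Safety labs and ECG are scheduled at baseline and Week 4 only (6.2.3.5, 6.2.3.6). Section 8.3 prescribes no ECG analysis.

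**SAP, laboratory.** Section 9.2 plans three outputs.
- Tables: "Shift from baseline in laboratory parameter results (indicated as Low, Normal, or High) will be summarized for each post-baseline visit". These are Tables 14.3.4.1 and 14.3.4.2.
- Figures: "Mean (+/- SD) laboratory parameter values will be graphically presented over time by treatment".
- Listings: "All laboratory parameters will be listed and include indicators for low/high and clinical significance as determined by the investigator".

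No table gives a numeric laboratory value or a change from baseline. Vital signs do get such a table (SAP 9.3, Table 14.3.4.3), and Appendix A already defines change from baseline.

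**SAP, ECG.** Section 9.4 plans a shift table of the overall interpretation, mean plots of the continuous parameters, a listing, and QTcF categories split at 450 msec for men and 470 msec for women. Change in QTcF has two categories, "Change from baseline <=60 msec (only applies to Week 4") and its complement above 60 msec. There is no numeric table of QTcF change.

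**The concern.** The protocol promises a numeric summary and the SAP does not deliver it. The SAP may modify the protocol's analysis (Protocol section 8 says that it will contain any modifications), but this one is neither stated nor explained. Because vital signs keep the numeric table, it reads as an oversight.

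The loss falls on the outcomes that matter most for this drug. A shift table cannot show a large fall inside the normal range, and it puts a value just under the limit in the same cell as a severe cytopenia. A single 60 msec cut shows almost nothing of a moderate rise in QTcF. With one scheduled post-baseline measurement and target arms of 150 and 75, within-person change is the most informative quantity collected, and no table reports it.

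**Working it through.** **Plan's own figure.** The documents give no precision or power figure for labs or QTcF. The one power figure, 80.8% in Protocol 8.7, concerns infection rates and is not used here.

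**Step 1. Protocol against SAP.**

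| Data | Protocol 8.3 | Numeric change table in SAP |
|---|---|---|
| Hematology, chemistry | Values and changes: mean, median, min, max | None |
| Vital signs | Not prescribed in 8.3 | Table 14.3.4.3 |
| QTcF | Not prescribed in 8.3 | None |

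The laboratory row is an unexplained departure. The QTcF row is a gap in SAP detail only.

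**Step 2. What the categories hide in one participant.**
- QTcF, using the SAP's cut-offs: a man going from 391 to 391 + 59 = 450 msec, or a woman from 411 to 411 + 59 = 470 msec, sits in the favourable category for both absolute value and change.
- Platelets, with an assumed normal range of 150-400 x 10^9/L: a fall from 390 to 155 is 235/390 = 60%, and reads Normal to Normal. In an arm of 150 it moves the mean by 235/150 = 1.6, which a plot of means would not show. The minimum change that Protocol 8.3.2 requires would show it as -235.

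**Step 3. What the categories hide between arms.** Neither document plans a test of these data; power at two-sided alpha 0.05 serves only to measure how much information each summary carries. Arm sizes of 150 and 75 are the protocol's targets. All other inputs are assumptions.

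*Platelets.* Assume baseline mean 250 and SD 55, lower limit 150, within-person change SD 35 (x 10^9/L). The standard error of the difference in mean change is 35 x sqrt(1/150 + 1/75) = 35 x 0.1414 = 4.95. For a fall of 20, power = Phi(20/4.95 - 1.96) = Phi(2.08) = 98%. The shift column simulates Normal-to-Low rates among those normal at baseline and applies Fisher's exact test, taking every participant as normal at baseline.

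| True mean fall | Normal to Low, placebo | Normal to Low, GLS-1200 | Power, shift | Power, mean change |
|---|---|---|---|---|
| 15 | 4.0% | 7.0% | 9% | 86% |
| 20 | 4.0% | 8.3% | 16% | 98% |
| 30 | 4.0% | 11.4% | 42% | >99% |

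With a change SD of 30 to 50, the mean difference detectable at 80% power is (1.96 + 0.84) x SD x 0.1414, or about 12 to 20.

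*QTcF.* Assume a true mean rise of 10 msec on GLS-1200. The expected number above 60 msec among 150 is 150 x [1 - Phi((60 - 10)/SD)].

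| Change SD (msec) | Expected above 60 msec of 150 | Power, mean change |
|---|---|---|
| 12 | 0.002 | >99% |
| 15 | 0.06 | >99% |
| 20 | 0.9 | 94% |

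From tabulated means and SDs of change, a reader could form a 95% interval for the difference with half-width 1.96 x SD x 0.1414: 2.8, 4.2 and 5.5 msec for SD 10, 15 and 20.

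**Step 4. Do the plots fill the gap?** In part. With complete pairs, the difference between the two plotted means equals the mean change. The SD of change cannot be recovered, because it depends on the within-person correlation. In the platelet example the Week 4 SD is sqrt(55^2 + 35^2) = 65.2. A reader who treats the two plotted points as independent gets a change SD of sqrt(55^2 + 65.2^2) = 85.3 instead of 35. The half-width for the difference between arms then becomes 1.96 x 85.3 x 0.1414 = 23.6 instead of 9.7, and a difference of 20 looks like noise.

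**The case against.** A reader might infer that the SAP reduces labs to shifts and QTcF to one cut, so that quinine toxicity could go undetected. The documents do not support that. SAP 9.2 also plans mean plots by arm and full listings. SAP 9.4 adds the sex-specific category ">450 msec (males) or >470 msec (females"), the interpretation shift table and mean plots. The individuals in Step 2 would appear in the listings. Protocol 7.1.6 says "Grade 2 and higher laboratory abnormalities (e.g., serum chemistry, CBC) are to be recorded". Grade 3 or higher laboratory abnormalities go to the sponsor within 24 hours (7.3.1) and, if related, count toward the stopping rules (7.3.2). Treatment-emergent events are tabulated by severity. All of this stands.

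Three further points have weight.
- Section 1.1.2 of the protocol classes thrombocytopenia with idiosyncratic reactions, so individual outliers may be the likelier signal than a shift in means. That tempers the platelet power comparison. It does not remove the need for the numeric table, whose minimum and maximum change show outliers by arm.
- The named effects belong to oral quinine; exposure here is 6 mg/day.
- No ECG analysis was promised, so finer QTcF categories, a confidence interval between arms and a table of worst grade go beyond the protocol.

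The safety nets do not replace the missing summary. A laboratory abnormality becomes an adverse event only if it meets a criterion in Protocol 7.1.6, and 7.1.1 excludes those considered non-significant. No SAP laboratory table reports grade. Listings do not compare arms.

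**Conclusion.** The point holds as an unexplained omission. SAP 9.2 and Tables 14.3.4.1-2 leave out the numeric laboratory summary that Protocol 8.3.2 requires. QTcF also lacks a numeric change table, but that is a weakness of the SAP and not a broken commitment.

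The consequence is reduced sensitivity and no numeric comparison by arm for effects that the protocol itself names, under a primary safety objective. It is not blindness to toxicity. The omission itself rests on the documents alone. The size of the lost sensitivity (16% against 98% power for a mean platelet fall of 20; fewer than one participant expected above 60 msec for a 10 msec QTcF rise) rests on assumed distributions and true shifts that the documents do not give. The primary efficacy test is unaffected. The tables should be corrected before the analysis is run.

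**What to change.** **Needed.** In SAP 9.2, add a table of observed value and change from baseline (n, mean, SD, median, minimum, maximum) by arm for each hematology and chemistry test, in the Table 14.3.4.3 layout, and enter it in Appendices B and C. Keep the shift tables. If the sponsor prefers to omit the summary, the SAP should state and justify the departure from Protocol 8.3.2.

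**Cheap addition.** In SAP 9.4, add the same descriptive table for QTcF.

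**Optional.** An intermediate QTcF change category, a 95% confidence interval for the difference between arms in mean change, and a table of worst CTCAE grade for platelets and hemoglobin.

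**Cost.** A few lines of SAP text and two or three tables that reuse an existing shell and a derivation already in Appendix A. No new data, visits or tests.
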